10.4.5. ADHERENCE AND RETENTION ANALYSES

Protocol deviations will be tabulated. Baseline demographic and medical history will be tabulated by whether the 6 month NOSE score data are available or missing to identify potential systematic differences between subjects with and without 6 month follow-up scores.

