5. STUDY ENROLLMENT AND WITHDRAWAL

5.1. PARTICIPANT INCLUSION CRITERIA

In order to be eligible to participate in this study, an individual must meet all of the following inclusion criteria:

1. The subject has NOSE Score ≥ 55 .
2. The subject has dynamic lateral nasal wall insufficiency as confirmed by Positive Modified Cottle Maneuver.
3. The subject is ≥ 18 years of age.
4. The subject is willing and able to provide informed consent and comply with the study protocol.
5. The subject is seeking treatment for nasal airway obstruction due to Nasal Valve Collapse (NVC) and is willing to undergo an in-office nasal implant procedure alone or with a turbinate reduction procedure.
6. The subject has appropriate nasal and facial anatomy to receive the Latera Implant.
7. The subject agrees to follow-up examinations through twelve (12) months post operatively.
8. The subject has failed to benefit from appropriate maximal medical management [e.g., nasal steroids (at least 4 weeks); antihistamines; oral decongestants; nasal strips, stents, or cones]. Failure of maximal medical management may be from lack of effectiveness or tolerability.

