5.3. STRATEGIES FOR RECRUITMENT AND RETENTION

A maximum of 250 subjects will be enrolled in the study. Up to 170 of these will be enrolled to reach target of 150 subjects completing the 24 months follow up. Up to 80 additional subjects will be enrolled as training cases. It is anticipated that this enrollment will take place in the initial 8 months of the study after study start-up. Subjects will be enrolled at approximately 25 individual sites within the United States.

Subjects will be recruited from sites' existing patient populations that are seeking treatment for nasal airway obstruction including nasal valve collapse. Anatomical considerations may impact the race distribution (e.g. some races may be less prone to lateral wall collapse), but the intention is to enroll all eligible subjects. Based on an earlier study with the device, both genders are expected to be well represented in the study.

Study brochures containing information on study participation and the Implant may be provided to the sites, as well as posters that may be displayed either as hard copies or electronically on computer monitors in the office.

The following tools will be utilized to encourage subjects' compliance to the study visit schedule:

- Subjects enrolled as training cases may receive a stipend for their time and to cover travel costs. Subjects must complete the study through the 1 month visit and will receive \$100 prepaid debit card at the end of the 1 month visit.
- All other subjects may receive a stipend for their time and to cover travel costs as outlined below.
 - Subjects who complete the study full 24 month follow up are eligible for a total stipend of \$700.00 to be paid over a two year period. Upon completion of the Baseline, 1 Month, 3 Month, 6 Month, 12 Month, 18 Month and 24 Month visits, subjects will receive a \$100.00 prepaid debit card at each visit or follow up. The 18 Month and 24 Month follow up evaluations will be conducted in one of the following manners: office visit, telephone interview, completion of form by subject and mailed to office for data entry, depending on subject availability.
- Additionally, subjects will be contacted by phone, and where available automated texting and email, for both reminders to schedule or confirm upcoming study visits and as reminders for visits that have already been scheduled.

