7.7.2. Non-Training Cases - Schedule of Events Table

Study Events	Screening & Enrollment (Visit 1)	Baseline Evaluation (Visit 2) ¹	Treatment (Visit 3) ²	Follow Up 1 mo (Visit 4)	Follow Up 3 mo (Visit 5)	Follow Up 6 mo (Visit 6)	Follow Up 12 mo/Final Study Visit (Visit 7)	Follow Up 18 & 24 mo/Final Study Visit (Visits 8 & 9)	Early Exit
Secure Informed Consent	X								
Secure Re-Consent for 18M and 24M Follow Up									
Inclusion/Exclusion	X	X							
Pregnancy Test ³	X	X	X	X	X	X	X	X	
NOSE Scale (PRO)	X	X	X	X	X	X	X	X	
Modified Cottle Maneuver	X	X							
Epworth Sleepiness Scale (PRO)	X		X	X	X	X	X	X	
Subject Satisfaction Questionnaire (PRO)			X	X	X	X	X	X	
Health Economics Questionnaire (PRO)	X		X	X	X	X	X	X	
Demographics & Nasal Medical History	X								
Nasal Exam	X		X	X	X	X	X	X	
Lateral Wall Motion Video	X		X	X	X	X	X	X	
Photography- 3D Camera (select sites)	X			X	X	X	X	X	
Photography -Cosmetic (select sites)	X			X	X	X	X	X	
NAO Breathing Assessment (PRO)	X			X	X	X	X	X	
Assessment of Turbinite Contribution to NAO	X								
Photography - Planning Images			X						
NAO Treatment		X							
Concomitant Medications	X	X	X	X	X	X	X	X	
Adverse Event Assessment	X	X	X	X	X	X	X	X	
Adverse Device Effects Assessment									
Complete Study Exit Form							X ⁵	X	

¹ Visit 2 activities may be done in conjunction with Study Visit 1. In this instance, the Screening NOSE Scale is not required.

² If Visit 3 (Treatment Visit) is more than 1 month after Visit 1, inclusion/exclusion criteria need to be re-confirmed. Additionally, subjects should be asked to review IC form, initial and date the IC document to confirm continued consent for participation, and complete NOSE scale.

³ Female subjects of childbearing potential

⁴ If Visits 1, 2 and 3 are completed on the same day, the Screening and Treatment NOSE Scales are not required.

⁵ To be completed at 24M follow up.

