10.4.3. ANALYSIS OF THE SECONDARY ENDPOINT(S)

Response proportion as defined in section 10.4.2 will be evaluated for the 1, 3, 12, 18 and 24 month follow-up visits using the same technique as described for the primary endpoint.

Change in nasal airway obstruction from baseline at 1, 3, 6, 12, 18 and 24 months post-procedure as reported by subjects on a VAS 0-100 mm scale (0= no difficulty breathing through nose; 100mm=not-able to breathe through nose) will be analyzed using a mixed model for repeated measures (MMRM). Least-square mean change from baseline and corresponding 95% confidence intervals will be reported.

Baseline VAS score will be analyzed in a separate model, including decongestant use as a covariate. Decongestant use will be considered at baseline only to visualize the turbinate contribution to overall obstruction, thus no decongestant VAS will be assessed at the follow-up visits.

Results from the subject satisfaction questionnaire will be tabulated at 6 months. Sensitivity analyses for missing data will be described in the SAP.

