10.4.4. SAFETY ANALYSES

Two analysis sets will be used to summarize adverse events. The ITT analysis set will be used to summarize acute adverse events (through 1 month post procedure), and the mITT analysis set will be used to summarize adverse events over the entire duration of follow-up. The primary safety reporting time-point is 6 months post-implant.

The overall incidence (i.e., number and percent of subjects with 1 or more adverse event) of adverse events, serious adverse device events, serious adverse events, fatal adverse events, and device related events (e.g., possibly, probably or definitely related) will be calculated for the acute phase, through 6 months post-procedure and for the entire duration of follow-up. The overall incidence of mild, moderate and severe events will be calculated by considering the most severe event for each subject.

In addition, the overall incidence for each adverse event type will be calculated. The adverse event types will be classified as defined in section 8.1.1

The implant retrieval rate will be calculated based on the number of implants retrievals per the total number of implants placed.

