Appendix I – PROTOCOL REVISION HISTORY

Version	Date	Significant Revisions
1.0	11Oct2016	Initial Protocol Release
1.1	24Oct2016	
Clarification of pregnancy testing population and procedure.Defining Training Case completion criteria.Minor administrative corrections.Administrative corrections and clarifications.
2.0	February 15, 2017	
Revised to improve content organization, provide clarity and enable better referencing. All addendums have been renamed as appendices and incorporated into this documentAdded allowance to replace implants.Added exclusion criteria #21 to allow for investigator's discretion to exclude a subject for unanticipated reasons.Number of sites increased to 25 to ensure timely trial completion.Added option to obtain discretionary images or videos such as documentation of implantation technique or adverse events (e.g. hematoma).Increased frequency of Lateral Wall Motion Video collection from baseline and 6 months to also include 1, 3, and 12 months follow up.Added endoscopic assessment of turbinate hypertrophy and septal deviation at 1, 3, 6 and 12 months to evaluate if there is any residual contribution of these post-surgery at all time pointsAdded optional procedure to collect endoscopic videos in conjunction with air flow measurements
2.1	07Sept2017	
Addition of 18 month and 24 month follow up evaluations

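### Follow-up beyond 12 months was added by amendment, yet the retention check stops at 6 months and late adverse events are a crude percentage of all implanted subjects

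*Combined protocol and SAP*

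**What the plan says.** - **Extension.** Appendix I lists, for version 2.1 (07Sept2017), "Addition of 18 month and 24 month follow up evaluations". Version 1.0 is dated 11Oct2016. The non-training schedule (Section 7.7.2) has a row "Secure Re-Consent for 18M and 24M Follow Up". Inclusion criterion 7 (Section 5.1) still reads "The subject agrees to follow-up examinations through twelve (12) months post operatively".
- **Late efficacy.** Response at 18 and 24 months is a secondary endpoint (Section 4.2.2). Under Section 10.4.3, response "will be evaluated for the 1, 3, 12, 18 and 24 month follow-up visits using the same technique as described for the primary endpoint". VAS change is analysed by MMRM.
- **Retention.** Section 10.4.5 has baseline demographics and medical history "tabulated by whether the 6 month NOSE score data are available or missing". No later visit is named.
- **Safety.** Section 10.4.4 defines incidence as "number and percent of subjects with 1 or more adverse event" and uses mITT for the full follow-up. It names no time-at-risk or time-to-event method.
- **Late event collection.** Section 7.1.5 limits collection after the 12-month visit to adverse device effects. Section 4.2.2 (endpoint 4) and Sections 8.1 and 8.3 describe wider collection through the end of participation.

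**The concern.** A subject who agreed to 12 months and is later asked to continue already has some experience of the result. If satisfied subjects agree more readily, the 18- and 24-month response rates describe a favourable subset. A comparison keyed to the 6-month NOSE score cannot detect this, because most subjects who decline the extension will have a 6-month score.

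On safety, a subject who leaves at month 12 stays in the mITT denominator but can contribute no later event, so the percentage through 24 months is too low.

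These visits matter for interpretation. The implant is said to absorb over about 18 months (Section 6.2), so months 18 to 24 carry the study's evidence on durability after absorption.

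**Working it through.** **1. The plan's own retention figures.** Section 5.3 aims for 150 of up to 170 main-study subjects completing 24 months: 150/170 = 88.2%. Section 10.5 reaches 170 by allowing about 10% drop-out around 150 subjects with *6-month* data: 150/0.90 = 167, in line with 170. The same 150 of 170 thus serves both 6 and 24 months, with no separate allowance for subjects who decline the extension. In the earlier German study (Section 2.2), 15 of 30 subjects (50%) completed 18 months, and three left after other nasal surgery, two of them after the 12-month visit. I use 88.2% as the planned case and 50% as a low case.

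**2. Who faces a second choice.** Section 5.3 says "It is anticipated that this enrollment will take place in the initial 8 months of the study after study start-up". Version 2.1 came about 11 months after version 1.0. If enrolment kept to that plan and started soon after version 1.0, most or all main-study subjects first consented to 12 months. Actual enrolment dates are not given.

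**3. Crude adverse-event percentage.** Let E be the risk to month 12, L the further risk from month 12 to 24 (both as shares of all subjects), and f the fraction still followed after month 12. Assume leaving is unrelated to late-event risk. Then crude percentage = E + L × f, against a true E + L.
- Assumed E = 5%, L = 5%, true 10%:
  - f = 150/170: 5 + 5 × 0.882 = **9.4%**
  - f = 0.50: 5 + 5 × 0.50 = **7.5%**
- Assumed E = 9%, L = 1%, true 10%:
  - f = 150/170: 9 + 1 × 0.882 = 9.9%
  - f = 0.50: 9 + 1 × 0.50 = 9.5%

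The understatement is L × (1 − f), so it is small if few events are late.

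A censored estimate removes it under the same assumption. With f = 0.50, late events are 2.5% of mITT among 95% × 0.50 = 47.5% still at risk, a conditional risk of 2.5/47.5 = 5.26%. Cumulative incidence is then 1 − 0.95 × (1 − 0.0526) = 10%.

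**4. Response.** Overstatement = share missing × (response in those observed − response in those missing).
- 20% missing, 10-point gap: 0.20 × 0.10 = **2 points**
- 40% missing, 30-point gap: 0.40 × 0.30 = **12 points**

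As a direct selection example, take a true response of 66% (the Section 10.5 planning value, borrowed here). If 90% of responders and 70% of non-responders continue, observed response is 0.594/(0.594 + 0.238) = 71.4%.

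**5. What the missing data leave open.** Suppose about 66% of those observed respond, out of 170, with all missing counted first as non-response and then as response.
- 150 observed (99 respond): 99/170 = 58.2% to 119/170 = 70.0%
- 136 observed (90 respond): 90/170 = 52.9% to 124/170 = 72.9%
- 85 observed (56 respond): 56/170 = 32.9% to 141/170 = 82.9%

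**The case against.** The strongest case against has four parts.

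- **The re-consent premise is thin.** It rests on one row label whose column marks are not legible in the text. A reader might infer that all 18- and 24-month data come only from re-consented subjects, or that the choice falls at month 12 once the outcome is settled. The documents support neither. They do not say when re-consent occurs or who needs it. With staggered enrolment some subjects could re-consent well before month 12, and anyone first consented under version 2.1 would need no second decision. What stands is narrower: for subjects consented under earlier versions, continuing is a further choice.
- **Missing data are not ignored.** A reader might infer that nothing covers late missingness. Section 10.4.3 carries the primary technique to these visits, and Section 10.4.2 lists missing-as-non-response among its possible sensitivity analyses. Section 10.4.3 also defers missing-data sensitivity analyses to the SAP. MMRM uses all available VAS data under missing at random. But the Section 10.4.2 list is optional and sits under the primary endpoint. None of these provisions describes who continued or corrects the event denominator.
- **The endpoints are supportive.** Section 10.4.9 says so, and Section 10.4.4 sets the primary safety time point at 6 months. This is correct and limits the weight of the point.
- **The size is assumed.** Retention may be good: Section 5.3 allows telephone or postal follow-up at 18 and 24 months and pays a stipend at each. Device events may also be mostly early, since Section 2.2 links the earlier study's three retrievals to technique or first-week manipulation. Both would shrink the bias, but neither shows that the remaining loss is unselective.

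**Conclusion.** The point holds as a worthwhile, inexpensive improvement. The plan adds a late follow-up phase that some subjects must choose to enter, but it has no check on who enters and no event measure that allows for those who do not.

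Under the assumptions above, a 10% device-related risk would be reported as 9.4% at planned retention and 7.5% at 50%, with less bias if few events are late. Response could be overstated by 2 to 12 points. These are illustrations: the re-consent rate, the response gap and the timing of events are not in the documents. A reader might take a heavier loss as the base case; two-thirds retention, for example, would give about 8.3%. The only planned figure is 150 of 170.

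It would also go too far to say that bias has been shown, or that it reaches the primary analysis. The 6-month efficacy and safety conclusions are unaffected.

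**What to change.** 1. Extend Section 10.4.5 to compare subjects with and without NOSE scores at 18 and at 24 months, on baseline characteristics and on 12-month response.
2. Commit to reporting 18- and 24-month response both as observed and with missing counted as non-response in mITT.
3. For adverse device effects only, add a Kaplan-Meier cumulative incidence to 24 months beside the crude percentage, with censoring at last contact and numbers at risk. State the non-informative-censoring assumption: if those who leave carry higher risk, this estimate is also too low. The comparison in item 1 helps to judge that.
4. Reconcile Section 7.1.5 with Sections 4.2.2, 8.1 and 8.3 before reporting any all-event 24-month rate. Otherwise that rate would mix two collection rules, and censoring would not repair it.

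The 12-month NOSE score (Section 7.1.5) and event onset dates (Section 8.1) are already collected, and Section 10.1 has the SAP finalised before database lock. Items 1 to 3 therefore need only SAP wording and a few extra tables; item 4 needs the protocol sections aligned. The downside is that late results may look less favourable.

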10.4.6. BASELINE DESCRIPTIVE STATISTICS

Baseline characteristics, including demographic characteristics, medical history, patient-reported outcomes and physical measurements will be summarized using descriptive statistics.

10.4.7. PLANNED INTERIM ANALYSES

No interim analyses with formal stopping implications will be performed, though changes in NOSE score may be aggregated to facilitate sample size calculations for future studies.

10.4.7.1. INTERIM ANALYSES

No interim analyses with formal stopping implications will be performed, though changes in NOSE score may be aggregated prior to database lock to facilitate sample size calculations for future studies. As there is no opportunity to stop early for efficacy or to alter the study design based on this calculation, there will be no type 1 error adjustment for this analysis.

10.4.8. ADDITIONAL SUB-GROUP ANALYSES

Response percentage, change in NOSE scores and other variables including satisfaction will also be evaluated in the following subgroups:

- Turbinate reduction method - radiofrequency versus mechanical
- Time-dependent presence or absence of allergic rhinitis
- Nasal geometry factors
 - Nose length (above or below median)
 - Nose width (above or below median)
 - Categorical skin thickness

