4.2.3. EXPLORATORY ENDPOINTS

Exploratory endpoints for informational purposes only:

1. Index procedure resource utilization: Anesthesia, procedure time and time to discharge.
2. Follow up resource utilization: Nasal airway obstruction related return visits and medication utilization.
3. Subject satisfaction questionnaire at 1, 3, and 12 months.
4. Degree of nasal airway obstruction as reported by subjects on the VAS scale at baseline with decongestant use.
5. Endoscopic lateral wall insufficiency score per side²¹ at baseline 1, 3, 6 and 12 months.
6. 3-D camera lateral wall motion assessment per side at baseline and 3, 6, and 12 months (at select sites).
7. Cosmesis changes from baseline evaluated by Independent Photo Review at 3 and 6 months (at select sites).
8. Change in subject sleepiness scale from baseline to 1, 3, 6, and 12 months as reported by subjects on the Epworth Sleepiness Scale (ESS).
9. Allergic rhinitis status at 1, 3, 6, and 12 months.
10. Nasal geometry: length of nose, height and width of nose, skin thickness of lateral wall at baseline.
11. Type of turbinate procedure.

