7.2. STUDY EVALUATIONS METHODS

7.2.1. Nasal Obstruction Symptom Evaluation (NOSE) Scale

The Nasal Obstruction Symptom Evaluation (NOSE) Scale¹⁸ is a Patient-Reported Outcome (PRO) instrument that will be administered to capture subject perception of the degree of nasal airway patency.

The NOSE scale will be completed at the Screening, Baseline, 1 Month, 3 Month, 6 Month, 12 Month, 18 Month and 24 Month visits. In the event that the Screening & Baseline Visits occur on the same day, only one NOSE score is required. The NOSE scale may additionally be completed at the Treatment Visit if more than one (1) month from Screening Visit.

The NOSE scale is a validated instrument, which was developed by the American Academy of Otolaryngology—Head and Neck Surgery (AAO-HNS), and has been used in several clinical trials. The scale is brief, easy to complete, and is an important tool for pre- and post-intervention evaluation of symptoms in subjects with nasal obstruction. NOSE Scale allows subjects to quantify their symptoms based on the severity of obstruction.

Subjects will be asked: "Since your last follow up visit, how much of a problem were the following conditions for you?" Specifically, subjects will be asked to rate their perceptions on the Likert scale with respect to the following characteristics:

- Nasal congestion or stuffiness
- Nasal blockage or obstruction
- Trouble breathing through my nose
- Trouble sleeping
- Unable to get enough air through my nose during exercise or exertion

Subjects will rate their responses using a Likert scale with response options 0, 1, 2, 3 or 4, as follows:

- (0) Not a Problem
- (1) Very Mild Problem
- (2) Moderate problem
- (3) Fairly Bad Problem
- (4) Severe problem

The responses are rated along the continuum, with a rating of “0 – not a problem” indicating no problem breathing, with a completely free flow of air through the nasal airway; “1 – very mild problem”, with only slight obstruction in airflow; “2 – moderate problem”, with mouth breathing considered easier; “3 – fairly bad problem,” with considerable obstruction to airflow; and a rating of “4 – severe problem,” with complete blockage and obstruction of the nasal passageway, where the subject cannot breathe through the nose and can only mouth breathe. A copy of the Nasal Obstruction Symptom Evaluation Scale questionnaire is attached (See Appendix V).

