7.2.6. Demographics & Nasal Medical History

Demographic information, such as age, gender, ethnicity, race and date of onset of nasal obstruction will be ascertained for all subjects at the Baseline Visit.

The past five years of relevant nasal medical history will include a complete review of nasal systems and evaluation of symptoms, including an assessment of nasal airway obstruction signs and symptoms. A history of prior nasal trauma or nasal surgery will be noted, as well as other medical conditions related to head and neck and respiratory conditions. Questions will be asked about the medications used by the subjects,

including the types and doses of medications that are used to control nasal obstruction symptoms and the performance of those medications in controlling their symptoms (i.e., OTC medications, nasal sprays, decongestants, nasal airway devices, etc.).

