10.4.2. ANALYSIS OF THE PRIMARY EFFICACY ENDPOINT(S)

The primary endpoint will be the proportion of treatment responders at 6 months post procedure. The mITT analysis dataset will be used to analyze the primary endpoint.

Responder is defined as a subject that has at least one (1) NOSE class improvement or at least 20% NOSE score reduction compared to baseline.

Subjects will be classified as non-responders if neither of these criteria is met.

NOSE score is a PRO instrument which measures the impact of nasal obstruction on quality of life. It is scored in increments of 5 points, and the total score is calculated as the sum of all 5 questions multiplied by 5, where the range is 0 (asymptomatic) to 100 (most extreme deleterious impact on quality of life). The NOSE score classes¹⁷ are based on the total calculated score:

- Mild:** 5 – 25 points
- Moderate:** 30 – 50 points
- Severe:** 55 – 75 points
- Extreme:** 80 – 100 points

This primary hypothesis will be evaluated for the mITT using a -2-sided exact test²³, and the corresponding exact (Clopper-Pearson) 2-sided 95% confidence interval will be calculated. The null hypothesis that the proportion of responders is $\neq 0.5$ will be rejected if the p-value is < 0.05 .

Sensitivity analyses will be conducted to determine the impact of missing data on these results. These analyses will depend on the extent of missing data, and will be detailed in the SAP, but may include:

1. Last observation carried forward (LOCF)
2. Subjects with missing data classified as non-responders
3. Re-implanted subjects classified as non-responders

This analysis will be repeated for the Latera stand-alone Population alone. While this study is not sufficiently powered to reject the null hypothesis for this subgroup, the response rate, 95% confidence interval and p-value will be calculated. See section 10.5 for further details.

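### The allergic-rhinitis subgroup uses status recorded only after the procedure, with no stated diagnostic criterion, so it may depend on the NOSE outcome and cannot show which patients benefit

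*Combined protocol and SAP*

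**What the plan says.** Section 10.4.8 sets out the subgroup work: "Response percentage, change in NOSE scores and other variables including satisfaction will also be evaluated in the following subgroups". One of the factors is "Time-dependent presence or absence of allergic rhinitis".

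The rhinitis data are an exploratory item in section 4.2.3: "Allergic rhinitis status at 1, 3, 6, and 12 months". Every one of these time points follows the procedure. Other items in the same list name baseline where it is meant, for example "Nasal geometry: length of nose, height and width of nose, skin thickness of lateral wall at baseline"; nose length, nose width and skin thickness are also subgroup factors in section 10.4.8. The lateral wall insufficiency score and the Epworth scale likewise have a stated baseline.

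The outcome comes from the NOSE scale. Its first item in section 7.2.1 is "Nasal congestion or stuffiness", and two of the other four concern blockage and difficulty breathing through the nose. Section 10.4.2 turns the score into response: "Responder is defined as a subject that has at least one (1) NOSE class improvement or at least 20% NOSE score reduction compared to baseline".

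Section 7.2 describes no rhinitis assessment, and the documents give no diagnostic criterion. They do not say which visit's status is paired with which visit's outcome. Response is also analysed at 18 and 24 months (sections 4.2.2 and 10.4.3), where no rhinitis status is listed.

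**The concern.** A status that can change from visit to visit must describe disease at that visit, not a fixed history. Two routes could then link it to the outcome:

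- A subject who is still congested at 6 months may be recorded as having rhinitis because of that congestion.
- Rhinitis that is truly active at the visit may itself raise the NOSE score.

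Both routes would put more non-responders in the rhinitis-present group, even if having rhinitis beforehand made no difference to the result of the implant. The first is a labelling artefact. The second is a real concurrent association, but not a property of the patient known when the procedure is chosen.

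What is at stake is interpretation. A table showing lower response with rhinitis could be taken as guidance on whom to treat, and this definition cannot supply it.

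**Working it through.** **Plan's own figure.** The documents give no figure for this subgroup: no prevalence, no labelling error rate and no expected difference. From section 10.5 the illustration takes the design response rate (66%), the rate attributed to previous trials (80%) and the 150 subjects with 6-month data.

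**Illustration 1: label rates that differ by response.** Assumed: rhinitis has no true effect, and a rhinitis label at 6 months is given to 10% of responders and 20% of non-responders. With overall response R:

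- Response, rhinitis present = 0.10R / [0.10R + 0.20(1 − R)]
- Response, rhinitis absent = 0.90R / [0.90R + 0.80(1 − R)]

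At R = 0.66:

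- Present: 0.066 / (0.066 + 0.068) = 49%
- Absent: 0.594 / (0.594 + 0.272) = 69%
- Labelled present: 0.134 × 150, about 20 subjects

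At R = 0.80:

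- Present: 0.080 / (0.080 + 0.040) = 67%
- Absent: 0.720 / (0.720 + 0.160) = 82%
- Labelled present: 0.120 × 150 = 18 subjects

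**Illustration 2: true rhinitis plus outcome-related mislabelling.** Let true prevalence be p, independent of response. A share f of rhinitis-free non-responders is labelled present, and a share g of responders with rhinitis is labelled absent. Write q for the proportion labelled present:

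- q = pR(1 − g) + p(1 − R) + (1 − p)(1 − R)f
- Response, present = pR(1 − g) / q
- Response, absent = [(1 − p)R + pRg] / (1 − q)

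With p = 0.30, R = 0.66, f = 0.20 and g = 0:

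- q = 0.198 + 0.102 + 0.0476 = 0.3476, about 52 of 150
- Present: 0.198 / 0.3476 = 57.0%
- Absent: 0.462 / 0.6524 = 70.8%
- Gap: 13.9 points (from unrounded rates)

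| Assumed range | Gap at R = 66% | Gap at R = 80% |
|---|---|---|
| p 20–40%, f 10–40%, g 0–20% | 5.5 to 39.9 points | 4.0 to 32.3 points |
| p 20–40%, f = 0, g = 20% | 6.3 to 7.9 points | 4.6 to 5.7 points |
| f = g = 0 | 0 | 0 |

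Within this model the gap has the same sign whenever f or g is above zero, and vanishes only when labelling is unrelated to the outcome. Status fixed before the procedure cannot be altered by the outcome, which is the f = g = 0 row. The documents do not say where in these ranges the trial would fall.

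**The case against.** The case against has real force on several points.

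- **The mechanism is inferred.** With no criterion given, the documents do not show that a congested subject would be labelled as having rhinitis. That rhinitis shares symptoms with NOSE is general clinical knowledge. Eligibility gives some reason to expect limited mislabelling: subjects have obstruction due to nasal valve collapse and have failed medical management (section 5.1), and other contributing pathology is excluded (section 5.2). Congestion is one of five NOSE items, and a 20% reduction counts as response, so responders may stay congested too. This stands, and it limits the claim to possible over-representation.
- **Concurrent status is a legitimate question.** The stated objective (section 3) is to obtain outcomes data, not to predict response. Relating active rhinitis to symptoms at the same visit is reasonable description. This stands, so the visit-level table should be kept.
- **Inference is already restrained.** Exploratory endpoints are informational (section 4.2.3), the only formal hypothesis is the primary one (section 10.2), and everything else is supportive (section 10.4.9). Section 10.4.8 specifies no subgroup or interaction test. This keeps the point minor. But section 10.4.9 addresses multiplicity, and caution about type 1 error does not change how the groups are formed.
- **A baseline definition is not ready-made.** Section 7.2.6 does not name rhinitis. Allergy medication is a poor substitute, because the failed treatments in the entry criterion include "nasal steroids (at least 4 weeks); antihistamines; oral decongestants". This stands and shapes the fix.

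A reader might go further and infer that non-responders are sorted into the rhinitis group, or that the comparison must show lower response there. The documents do not support that: without a criterion, prevalence or labelling rates, neither the occurrence nor the size of the distortion can be established.

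**Conclusion.** The point holds as a minor improvement. The subgroup rests on a post-procedure status with no stated criterion and is compared on an outcome scored from nasal congestion and obstruction symptoms at the same visits. Non-responders may therefore be over-represented where rhinitis is recorded as present. Whatever the labelling accuracy, a status first known after treatment cannot show which patients benefit.

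The size is unknown. The gaps of about 19 points (66% overall) and 15 points (80% overall) in the first illustration rest wholly on the assumed 10% and 20% label rates. With about 20 labelled subjects the observed rate would also be imprecise: 10 of 20 has an exact 95% interval of roughly 27% to 73%.

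Nor should a reader infer that the main result is in doubt. The primary test, sample size, significance level and safety analyses do not use rhinitis status.

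**What to change.** In the SAP, which section 10.1 says will be finalised before database lock:

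1. Define the subgroup by allergic rhinitis at baseline, using a documented diagnosis in the nasal medical history. Section 7.2.6 already requires one: "The past five years of relevant nasal medical history will include a complete review of nasal systems and evaluation of symptoms". State the coding rule, and do not let allergy medication or congestion alone qualify.
2. Apply this fixed status to outcomes at every visit, including 18 and 24 months. This also settles which status goes with which outcome.
3. Report rhinitis status at 1, 3, 6 and 12 months in a separate table labelled as a descriptive, concurrent association, and state how it was determined at each visit.

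The cost is SAP wording and a review of existing history entries; no visit or subject is added. Baseline rhinitis is not a named field, so some subjects may be misclassified or unclassifiable. Seasonal variation would appear only descriptively. In a single-arm study the baseline split would still describe response by a pre-procedure characteristic, without a comparator.
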